4.0 Acronyms and Definitions

ADE	adverse device effect
ADL	activities of daily living
AE	adverse event
ASADE	anticipated serious adverse device effect
CRF	case report form
CIP	clinical investigation plan
CRO	contract research organization
COTS	commercial off the shelf
CA	competent authority
DSMB	data and safety monitoring board
EC	European commission
ESD	endo-Surgery Device
FA	full analysis (data set)
FDA	food and drug administration
GEBT	gastric emptying breath test
GCP	good clinical practice
GLP	good laboratory practice
IB	investigator's brochure
ICF	informed consent form

	Title: Evaluation of EndoZip™ System (AS) in Obese Patients who failed to reduce weight with non-surgical weight-loss methods	
	Document No: CL00003	Rev: 1.0

ICH	international Conference on Harmonisation
IEC	institutional ethics committee
IFU	instruction for use
IRB	institutional review board
ISF	investigator site file
ISO	international organization for standardization
mFA	modified full analysis (data set)
NCA	national competent authorities
PI	principal investigator
PP	per protocol (data set)
RA	regulatory authorities
SADE	serious adverse device effect
SAE	serious adverse event
SOP	standard operating procedure
USADE	unanticipated serious adverse device effect

5.0 Introduction

This document is a protocol for human research study. This study will be conducted in accordance with the applicable international standard of Good Clinical Practice, and institutional research policies and procedures.

	
Title: Evaluation of EndoZip™ System (AS) in Obese Patients who failed to reduce weight with non-surgical weight-loss methods
		
Document No: CL00003	Rev: 1.0	Page:	22 of 83

5.1 Background

5.1.1 Applicable epidemiological background

Obesity is a global epidemic. In the last few decades, obesity has gained significance as a worldwide health problem. The World Health Organization (WHO) estimated that approximately 1.5 billion adults (age 20 y or older) were overweight [1]. Currently, more than 30% of the US adult population is obese [2], which accounts for approximately 72 million obese Americans [3].

The morbidity associated with obesity is alarming serious health concern, with an increased incidence of metabolic syndrome, type 2 diabetes mellitus, hypertension, and many other comorbidities.

5.1.2 Available treatment modalities

There are several alternatives to for the treatment of obesity (BMI of $>30 \text{ kg/m}^2$), which can be divided into the following: non-surgical treatments, medical devices, and surgery. Each alternative has its own advantages and disadvantages. A patient should fully discuss these alternatives with his or her physician to select the method that best meets expectations and lifestyle.

Non-Surgical Treatments

Non-surgical treatments for obesity include:

- Diet, exercise, and behavioral modifications, and
- Prescription weight loss medications.

Several reports have suggested a rather high incidence of failure for obese patients to sustain long-term weight loss with any form of non-surgical treatment.

Intra-Gastric Balloons

Intra-gastric balloons are typically recommended for patients with a BMI $30-40 \text{ kg/m}^2$. It is a temporary non-surgical obesity treatment that induces short-term weight loss by placing a soft, elastomeric balloon in the stomach, thus partially filling the stomach to achieve satiety. The Balloon is removed 6-12 months after placement.

Obesity Surgery

Bariatric surgery is typically recommended for patients with a BMI of at least 40 kg/m^2 ,

	Title: Evaluation of EndoZip™ System (AS) in Obese Patients who failed to reduce weight with non-surgical weight-loss methods		
Document No: CL00003	Rev: 1.0	Page:	23 of 83

or a BMI of at least 35 kg/m² with one or more obesity-related comorbid conditions. The most common types of bariatric surgery are described below.

Roux-en-Y Gastric Bypass (RYGB)

In a gastric bypass, the surgeon first constructs a proximal gastric pouch and then creates an outlet from the pouch to a limb of the small bowel. This results in a bypass of most of the stomach and duodenum.

Vertical Sleeve Gastrectomy

Vertical sleeve gastrectomy is a procedure which reduces the size of the stomach by surgical removal of a large portion of the stomach. The open edges are then sutured together to form a sleeve. The size of the stomach is permanently reduced without bypassing the intestines. Unlike RYGB, the stomach is not bypassed and there is no malabsorption component.

Biliopancreatic Diversion Duodenal Switch

The biliopancreatic diversion with duodenal switch is a procedure in which stomach removal is restricted to the outer margin, leaving a stomach sleeve with the pylorus intact. The small intestine is divided with one end attached to the stomach pouch. The majority of the small intestine is bypassed.

Single Anastomosis (Omega Loop) Bypass “mini bypass”

The mini bypass is a procedure in which the surgeon will reduce the size or volume of the stomach, similar to the gastric sleeve. This sleeve is then connected to the intestine, bypassing up to 200cm of the upper part of the intestine.

In general, bariatric surgeries have shown, in multiple studies, to lead to significant and durable weight loss. However, it has been estimated that only 1% of eligible patients undergo bariatric surgery because of serious complications including perforation, hemorrhage, infections and bowel obstructions, limited access, cost, and patient preference [4].

5.1.3 Study Rationale

NiTiNotes Ltd. has developed the EndoZip System which offers obesity treatment by an operator-friendly endoscopic procedure generating an endoluminal gastroplasty that restricts the stomach and impairs motility.

	Title: Evaluation of EndoZip™ System (AS) in Obese Patients who failed to reduce weight with non-surgical weight-loss methods		
Document No: CL00003	Rev: 1.0	Page:	24 of 83

The EndoZip system is designed to allow for the creation of multiple internal gastric segmentations in the stomach by using an endoscopic approach. The system allows the forming of wall-to-wall longitudinal attachments of the anterior and posterior stomach walls, creating multiple plications within. Another important determinant which predicts a favorable safety outcome is the minimally invasive nature of the procedure.

The pre-clinical studies and initial human study (details are provided in 6.2 and 6.3), using an earlier configuration of the device, have proven to have excellent safety profile, and provided initial performance data.

The aim of this study is to evaluate the updated device configuration of EndoZip system to establish the long-term safety and further validate the efficacy claim in the intended population.

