3.0 Protocol Synopsis

Protocol Number	CL00003
Protocol Title	Evaluation of EndoZip™ System (AS) in Obese Patients who failed to reduce weight with non-surgical weight-loss methods
Study Sponsor	
NiTINotes, [name]
 
[contact]
 
[contact]

Sponsor Representative	
[name] VP QA, Regulatory and Medical Affairs

Study Type	Pilot study
Study Product	EndoZip™ System (AS)
Study Location	Europe, Israel
Study Centers	
 1. Hospital Universitario HM Sanchinarro, Madrid, SPAIN 2. Fondazione Policlinico Universitario Agostino Gemelli IRCCS (CERTT), Rome, Italy 3. Rabin Medical Center, Petah Tikva, Israel

	
Title: Evaluation of EndoZip™ System (AS) in Obese Patients who failed to reduce weight with non-surgical weight-loss methods
	
Document No: CL00003	Rev: 1.0	Page: 9 of 83

Investigators	
 1. [name] 2. [name] 3. [name]
Study Duration	The duration for each participant will be 12 months; the total study duration is expected to be approx. 18 months
Study Design	The study is planned as a multicenter, prospective, single-arm, open-label, controlled clinical trial.
Planned Visits	
 • Office visits: 1 week, and 1, 2, 4, 6, 8, 10, and 12 month(s) • Remote follow up (by Phone): 3, 5, 7, 9, and 11 month(s) • Endoscopy follow up: 2 and 6 months • Motility evaluation by Gastric Emptying Breath Test (GEBT): 6 months • Physical examination, vital signs, waist circumference and BMI: 1 week, 1, 2, 4, 6, 8, 10 and 12 months • Blood tests: 2, 6 and 12 months • IWQOL-Lite: 2, 6 and 12 months • Sleep Apnea (only for the relevant population): 2, 6 and 12 months
Patient Population	Male and Female with obesity, BMI of 30-40 kg/m ² , between the ages of 21 and 70 who failed to reduce weight with non-surgical weight-loss methods
Planned # of Patients	Up to 45 patients
Planned # of Sites	Up to 5 clinical sites
Planned # of Patients per Site	Up to 20

	Title: Evaluation of EndoZip™ System (AS) in Obese Patients who failed to reduce weight with non-surgical weight-loss methods	
Document No: CL00003	Rev: 1.0	Page: 10 of 83

Study Objective	
The objective of this study is to evaluate the safety and effectiveness of the EndoZip system procedure, coupled with lifestyle modifications, for weight reduction in obese patients with BMI of 30-40 kg/m².

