8.0 Study Objectives

8.1 Primary objectives

The evaluate the safety and effectiveness of the EndoZip system procedure, followed by lifestyle modifications, for weight reduction in obese patients with BMI of 30-40 kg/m².

8.2 Secondary objectives:

- To evaluate the potential improvement in patients' conditions.
- To evaluate the duration related to the EndoZip procedure.
- To evaluate physicians' satisfaction related to the EndoZip usability.

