14.0 Statistical Analysis

14.1 Sample Size Determination

This is a pilot study that will include up to 45 patients; no statistical considerations were made to determine the sample size.

The first two (2) patients per site will be considered as run-in period, to compensate for any learning curve that may be required for the EndoZip performance evaluation.

Safety evaluation will include all enrolled patients.

	Title: Evaluation of EndoZip™ System (AS) in Obese Patients who failed to reduce weight with non-surgical weight-loss methods		
Document No: CL00003	Rev: 1.0	Page:	53 of 83

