14.5 Safety Analysis

The cumulative incidence of adverse events observed during the procedure and throughout the follow-up period, will be presented in tabular format. A detailed list of all adverse events will be presented. The

	Title: Evaluation of EndoZip™ System (AS) in Obese Patients who failed to reduce weight with non-surgical weight-loss methods		
Document No: CL00003	Rev: 1.0	Page:	55 of 83

adverse event rate will be compiled with respect to seriousness, severity, expectedness and relationship to procedure and device. In addition, listings of all safety measures will be produced.

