15.11.1 Data Safety and Monitoring Board (DSMB)

An independent group of experts chosen by the sponsor will constitute the Data and Safety Monitoring Board (DSMB). The DSMB will review and adjudicate all serious device related and non-related adverse events and any other events deemed necessary. The Adverse Events will be reported

	Title: Evaluation of EndoZip™ System (AS) in Obese Patients who failed to reduce weight with non-surgical weight-loss methods		
Document No: CL00003	Rev: 1.0	Page:	60 of 83

as per the standard clinical practices. All adverse event incidence rates will be summarized by anticipation, severity and relationship to the investigational device.

The incidence of major complications using the EndoZip system will be presented.

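### Section 5.1.3 aims to establish long-term safety, but up to 45 patients over 12 months can only describe it, and no interval is assigned to safety rates

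*Combined protocol and SAP*

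**What the plan says.** Section 5.1.3 (Study Rationale) gives the aim as "to establish the long-term safety and further validate the efficacy claim" in the intended population. Section 8.1 words the primary objective more mildly: "The evaluate the safety and effectiveness of the EndoZip system procedure". The synopsis objective is also to evaluate, and section 9.1 places the safety summary under the primary endpoints.

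On size and duration, section 14.1 states: "This is a pilot study that will include up to 45 patients; no statistical considerations were made to determine the sample size". The synopsis states: "The duration for each participant will be 12 months".

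The safety analysis is in two places. Section 14.5 says: "The cumulative incidence of adverse events observed during the procedure and throughout the follow-up period, will be presented in tabular format". It adds event rates by seriousness, severity, expectedness and relationship, and closes: "In addition, listings of all safety measures will be produced". Section 15.11.1 says: "The incidence of major complications using the EndoZip system will be presented". Neither section names a confidence interval or an acceptable rate. By contrast, 14.4 gives the 5% responder rate an exact 95% interval. Section 14.6 gives 95% intervals for excess weight loss, BMI change, quality of life, procedure times, comorbidity changes and physician satisfaction.

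The safety set differs between sections. The synopsis uses the Full Analysis Set, which leaves out the first two patients at each site. Sections 14.1 and 14.2.1 use all enrolled patients, and 13.1.2 defines enrolment as signing the consent form.

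**The concern.** To establish safety, a study must be able to rule out event rates that would matter. This one was not sized to rule out any rate, sets no safety criterion, does not define long-term, and stops at 12 months. Section 7.2 lists perforation and obstruction needing an operation among the risks, so a serious-event rate of one or a few percent is not a trivial matter.

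If the final report gives counts and percentages alone, a zero in the serious-event row carries no statement of what it leaves open. Read beside the wording of 5.1.3, it could pass for demonstrated safety. The reader would have a stated precision for the usability questionnaire but not for a component of the primary objective.

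**Working it through.** **Inputs.** N is at most 45 (14.1) and follow-up is 12 months (synopsis). There are two run-in patients per site (10.0, 14.1) and three listed sites (synopsis). The documents give no expected complication rate, so the true rates in step 4 are illustrative assumptions.

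**1. Method check on the plan's own figure.** The sample size has no derivation to reproduce. The one binomial interval in the documents is in 6.3: 31 of 31 procedures completed, with a 95% interval of 89% to 100%. The exact (Clopper-Pearson) two-sided lower limit when all succeed is 0.025^(1/n). For n = 31 this is 0.888, which agrees with the stated 89%. The same method is used below.

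**2. Upper limit with no events, full sample.** The formula is 1 − 0.025^(1/n). For n = 45 it gives 0.0787, or 7.9%. One event in 45 (2.2%) has an exact interval of 0.06% to 11.8%.

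**3. The same limit under the synopsis safety set.** Run-in at three sites is 3 × 2 = 6, leaving 45 − 6 = 39. The limit is 1 − 0.025^(1/39) = 0.0903, or 9.0%.

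Under the body's rule the denominator is everyone who signed consent. That includes screen failures who were never treated and cannot have a procedure-related event, so the observed incidence is diluted. If the cap of 45 counts consents, fewer than 45 will be treated. Hence 7.9% is the smallest zero-event limit the design can give for treated patients.

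**4. Chance of seeing no event at all in 45 patients.** The formula is (1 − p)^45.

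| Assumed true rate p | No event seen | At least one seen |
|---|---|---|
| 1% | 64% | 36% |
| 2% | 40% | 60% |
| 3% | 25% | 75% |
| 5% | 10% | 90% |

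**5. Scale.** For a zero count to push the two-sided upper limit down to 2%, n must be at least ln(0.025)/ln(0.98) = 182.6, so 183 patients. That is about four times the planned maximum (183/45 = 4.1).

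**6. How the documents read an earlier small sample.** Section 6.3 reports no related adverse events in 11 patients. The upper limit for 0/11 is 1 − 0.025^(1/11) = 28.5%. Section 5.1.3 nevertheless treats the safety of the earlier configuration as proven from the pre-clinical work and that study. Section 6.3.1 then reports a serious adverse event in the study's expansion, which led to a redesign, and 7.1 says the extended study ended early.

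**The case against.** The strongest reply is that 5.1.3 is background. Its sentence itself opens with evaluating the updated configuration, and the sections that govern the analysis are modest. The study is labelled a pilot, 8.1 says evaluate, 14.2.2 calls the analyses mainly descriptive, and no success rule turns zero events into a claim. Serious events go to a DSMB, all events are listed, and anyone can compute an exact interval from the counts. All of this stands. It shows that one sentence in 5.1.3 is out of line with the rest, which supports rewording it and does not call the design into question.

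Section 14.2.3 also sets a general two-sided 95% level for intervals. It can be read as covering safety, but no safety section applies it. The accurate statement is that none is specified for safety rates, not that intervals are ruled out.

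Four stronger readings are tempting and are not supported:

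- **Safety alone lacks intervals.** A reader might infer that every effectiveness endpoint gets one. Section 14.6 has no analysis for gastric motility or sleep apnea, so the contrast is with the responder rate and most secondary endpoints.
- **A limit of 10.0% from 35 patients.** This needs five sites (45 − 10 = 35). Section 10.0 plans 10 to 20 patients per site, and 5 × 10 = 50 already exceeds 45. Even the 9.0% figure applies only under the synopsis safety set.
- **Complications of a few percent would probably be missed.** At an assumed 3%, at least one event is seen with probability 75%. Even at 2%, an event is more likely seen than not.
- **A clean result will be over-read.** That is a prediction. Step 6 of the working shows the tendency in this document, but nothing in the analysis plan commits the sponsor to it.

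**Conclusion.** The concern holds in a limited form. The aim in 5.1.3 exceeds what the design can deliver and departs from the protocol's own objective, and sections 14.5 and 15.11.1 leave the precision of the safety rates unstated. A result with no events would be compatible with a true rate of up to 7.9% in 45 patients, or about 9.0% in the 39 left under the synopsis set with three sites. These limits assume independent patients, complete 12-month follow-up and the maximum enrolment. Losses or screen failures within the 45 would widen them.

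No planned analysis is invalid and no decision rule is affected. What is at stake is the claim that the finished study can support.

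**What to change.** 1. In 5.1.3, restate the safety aim as describing safety to 12 months, in line with 8.1.
2. Define one safety set, worded identically in the synopsis, 14.1 and 14.2.1: all patients in whom the EndoZip procedure was started, run-in patients included. This differs from both current definitions. It keeps the learning-curve patients in the count and leaves untreated screen failures out.
3. In 14.5, report exact (Clopper-Pearson) two-sided 95% intervals for the patient-level incidence of SAEs, SADEs, and device- or procedure-related adverse events. Print the upper limit when the count is zero.

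The cost is a few sentences and a few table columns, with no added patients, visits or data. The downside for the sponsor is a less favourable safety statement, since even a clean result will carry an upper limit of about 8%.

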6.0 Investigational Device

6.1 General Description

The EndoZip™ is an automatic, operator-friendly Endo-Surgery Device (ESD) designed to create multiple internal gastric segmentations in the stomach by using an endoscopic approach. The system applies a wall-to-wall longitudinal attachment of the anterior and posterior stomach walls, creating multiple plications within.

The EndoZip is inserted to the stomach through a standard endoscopy designated Overtube. The device advancement and positioning in the stomach is visually guided by a small diameter endoscope inserted through device's dedicated channel. In addition, EndoZip is connected to a COTS (Commercial Off the Shelf) vacuum pump used in Endoscopy units / clinics.

The system with the aid of the external vacuum pump, enables the approximation of the opposite stomach walls by extracting air from the chosen deployment site, i.e., the creation of a near vacuum state, causing the tissue segments to draw into the Bougie and create a narrowing for segmentation of the stomach.

Following the approximation process, a custom designed needle is driven through the Bougie, (from its distal end toward its proximal end), passing the attached suture through the approximated tissue segments and creating the continuous plications within the stomach. Then the device enables tightening and cinching the approximated tissue segment with an integrated, dedicated clip. The procedure is completed with device retraction from the deployment site and a visual confirmation using a scope. The system provides suturing stage indication by a LED bar located in the device handle.

	
Title: Evaluation of EndoZip™ System (AS) in Obese Patients who failed to reduce weight with non-surgical weight-loss methods
	
Document No: CL00003	Rev: 1.0	Page: 25 of 83

Per the IFU, up to five (5) systems, per the physicians' judgement, may be used for the creation of multiple plications within the stomach. For the purpose of this study up to six (6) systems, per the physicians' judgement, may be used for the creation of multiple plications within the stomach.

The EndoZip™ System is made of biocompatible non absorbable materials widely used as surgical sutures. The system is supplied sterile.

In addition, the EndoZip™ System is a minimally invasive procedure, a reproducible and easy to use device that can aid the obesity treatment by expanding the access and acceptability to a broad population segment.

6.1.1 EndoZip Main components

The EndoZip system consists of a disposable device that controls the procedure and a reusable electrical power supply.

6.1.2 EndoZip Disposable Device

The EndoZip disposable device comprises three main components: Bougie, Insertion Tube and Handle as depicted in Figure 1 below.

[figure not shown]

Figure 1 – EndoZip Disposable Device

	Title: Evaluation of EndoZip™ System (AS) in Obese Patients who failed to reduce weight with non-surgical weight-loss methods		
Document No: CL00003	Rev: 1.0	Page:	26 of 83

Bougie

The distal end of the device, referred as the “Bougie”, is designed to optimize the suturing mechanism. It contains a chamber that captures the tissue using a vacuum, to support full-thickness sutures. In addition, the Bougie includes a steerable segment that facilitates device maneuvering.

Insertion Tube (IT)

The Insertion Tube (IT) connects the Handle and Bougie parts, supporting insertion and evacuation of air and CO₂. It also contains a channel for the endoscope passthrough.

EndoZip Handle

The EndoZip handle aids the physician to maneuver the device and position it in the desired abdominal area. In addition, it controls all suturing activity. The handle comprises 2 functional parts:

- Motor unit: Includes motors and controllers to perform all required activities including stitching, tightening, clipping, and cutting of suture wire. The unit has a sensing mechanism that ensures that the stages after stitching are contingent upon the needle reaching its designated area.
- Mechanical control unit: The mechanical control unit aids the physician to maneuver the device and position it in the desired abdominal area.

In addition, the EndoZip System comprises the following Disposable Components:

- pinch clamps – 2 pinch clamps used to manage the vacuum via the EndoZip and the endoscope during the procedure.
- Sealing Adaptor – A component located between the EndoZip system to the Overtube.

